8.1.5 Post Discharge Phone Visit

At 10 hours post the start of the ketamine infusion (plus/minus 2 hours) the patient will be assessed by a study investigator (in-person or called at home if subject were to be discharged). During this phone visit, the procedures listed in Table 3 (C-SSRS (since last visit), and an assessment of AEs) will be completed.

8.1.6 Randomization

Subjects will be assessed in person 24 hours post-infusion for response to ketamine. Those who do not respond will be provided standard of care for ongoing suicidal ideation. Following the documented observance of a therapeutic response to intravenous ketamine as defined by a 25% or greater reduction in the on the MADRS subset of the BISS score and a score of ≤ 3 on the C-SSRS at 24 hours post infusion, subjects will be randomized 2:1:1 to either a fixed dose combination of experimental drug NRX-101 (DCS + lurasidone), or to an identical capsule containing placebo + lurasidone, or to an identical capsule containing placebo. Randomization blocks will be allocated at the site level to ensure that treatment and control groups are balanced per site. An Interactive Web Response System will be used.

8.1.7 Early Termination Visit

If a subject withdraws consent, or is otherwise terminated from the study, every effort should be made by the site to perform the procedures listed for Day 70.

8.1.8 Post Ketamine Infusion Follow-Up

Subjects who are non-responders at 24 hours following the start of the ketamine infusion will be withdrawn from the study and treated according to the site’s standard treatment procedure. Non-response is defined as less than a 25% reduction on the MADRS subset of the BISS score and a score of ≥ 4 on the C-SSRS.

8.1.9 Concomitant Medications

All concomitant medications taken during the study will be recorded in the Concomitant Medication Log for each subject, along with dosage information and start and stop dates. Allowed concomitant medications include any prescription or over-the-counter medication not specifically excluded by the protocol (see Appendix 1), as well as stable, ongoing antidepressant or antipsychotic therapy and stable allowed hypnotic therapy. Subjects requiring excluded drugs will be discontinued from the study.

Prohibited concomitant medications which the patient and the study investigator agree may be discontinued, will be washed out for a period of 5 half lives or one week, whichever is longer. Clinically appropriate tapering regimens may be used if necessary. The screen period may be extended, upon consultation with the medical monitor, to allow for a sufficient washout period. A list of prohibited concomitant medications is included in Appendix 1.

8.1.10 Subject Recruitment

Subjects will be recruited through study clinicians from patients who present at the site with bipolar depression and suicidal ideation. Those deemed eligible will be scheduled for a screening visit with one of the study physicians at the site. Appropriate recruitment strategies such as advertising, primary care physician referrals and internet based outreach may be used as well. Any patient facing materials will be submitted for IRB approval.

8.1.11 Inclusion of Children

Adolescents between the ages of 18 and 21 will be eligible for enrollment. We are not including children younger than age 18. We have decided to exclude children under the age of 18 because there are specific safety considerations, as well as treatment considerations in pediatric bipolar depression that exceed the scope of this study. However, if treatments from this proposal are found efficacious and well tolerated, a next step may be the consideration of use in children of younger ages.

8.2 Procedures

8.2.1 Laboratory/Diagnostic Procedures

Clinical laboratory safety testing will be conducted locally by the study site using CLIA-approved laboratories that have been audited by study personnel for compliance. Once the subject has signed the informed consent document, the urine pregnancy test will be performed at the Screen Visit, and Visits 5 and 9. ECGs will be measured at the Screen Visit, the Baseline Visit (at the 24-hour time point), and at Visits 5 and 9. Chemistry and complete blood count (CBC) will also be obtained at the Screen Visit, and at Visits 5 and 9. Weight, BMI, oral temperature, seated pulse and seated blood pressure (vital signs) will be recorded at each visit. At

Screen, and Visit 5 and 10, subjects will have a physical examination. The laboratory tests required are listed in Table 4, below.

Table 4 Laboratory Assessments

Laboratory Test	Frequency
CBC	Screen, Visits 5 and 9
Chemistry (Total bilirubin, AST, ALT, GGT, ALK Phosphatase, Creatine, BUN/Urea, Glucose, Uric Acid)	Screen, Visits 5 and 9
HbA1c (only for diabetics)	Screen
Pregnancy Test	Screen, Visits 5 and 9
Urine Toxicity Screen	Screen, Visits 5 and 9

8.2.2 Drug Levels

Blood samples for monitoring therapeutic drug levels will be collected on all subjects to verify exposure and consistency with the randomization schedule. The timing of the blood draws are defined in Table 3 and include both pre-dosage (time 0) and post initial dosing of investigational product within the first 2 hours. Analyses of the samples will be conducted by the central laboratory.

8.2.3 Randomization phase

Following the documented observance of a therapeutic response to IV ketamine as defined by a 25% or greater reduction in the baseline MADRS and a C-SSRS ≤ 3 at 24 hours post infusion, subjects will be randomized 2:1:1 to either a fixed dose combination of experimental drug NRX-101 (DCS + lurasidone) or to an identical capsule containing placebo + lurasidone or to an identical capsule containing placebo. Institution balancing will be used to ensure that treatment and control groups are balanced with stratification according to C-SSRS 24 hours post-infusion (1, 2). Subjects who respond to ketamine will be followed for 6 weeks or until they require additional treatment.

8.2.4 Blinding Procedures

Investigational product will be provided in a blinded fashion to sites for dispensation to subjects.

8.2.5 Outcome and Safety Measures

8.2.5.1 Outcome Measures

8.2.5.1.1 Primary Efficacy Endpoint

The primary outcome measure will be time to relapse, defined as (1) a return to a score of ≥ 4 on the C-SSRS, (2) a score of ≥ 20 on the MADRS subset of the BISS following a response to

ketamine at 24 hours, or (3) the treating physician's determination that a change in treatment plan, such as re-hospitalization, ECT, or addition of new antidepressant drugs is required.

All site-defined relapses will be adjudicated by a Relapse Adjudication Committee (RAC) which will review documentation provided by the site for each incidence and determine whether the relapse meets the protocol definition of relapse. The RAC will meet monthly. The RAC is authorized to determine that relapse occurred even if the site does not make this determination.

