1. SYNOPSIS

Name of Investigational Product:	NRX-101 (administered to subjects who respond to an intravenous infusion of ketamine - 0.5 mg/kg administered over 40 min; on Day 0)
Name of Active Ingredient:	Fixed dose combination of d-cycloserine + lurasidone
Reference Product(s):	Lurasidone/placebo
Title of Study:	NRX-101 for the Treatment of Acute Suicidal Ideation and Behavior (ASIB) in Bipolar Depression
Phase of Development:	Phase 2b/3
Study Site(s):	Approximately 12 study sites which may be either inpatient psychiatric hospitals or community mental health centers/bipolar clinics with immediate access to inpatient care facilities. All sites will have a minimum of 12 months prior experience in the use of ketamine for stabilization of patients with ASIB in Bipolar Depression as part of their practice of medicine.
Study Duration:	Screening: up to 48 hours; IV ketamine Day 0; 6-week treatment; 4 week follow up
Background and Rationale:	DCS and Lurasidone, taken together, have been shown to maintain a 50% reduction in depression and a 75% reduction in suicidality following a single infusion of ketamine in patients with suicidal ideation and bipolar depression. Ketamine is increasingly used in medical practice to achieve rapid stabilization of patients with ASIB. However, the duration of ketamine effect is limited and its repeated use for maintenance of stabilization is not proven.
Objectives:	
The objectives of the study are as follows:
 
Primary Objective:
 
 The primary objective of the study is to test the hypothesis that following stabilization of depression and ASIB in response to initial ketamine infusion, NRX-101 is superior to lurasidone alone and also superior to placebo as oral-therapy for delaying time to relapse (resulting in a new treatment plan or the subject relapsing to baseline levels of depression or suicidality) in subjects with documented bipolar depression presenting with symptoms of depression and suicidal ideation. 
Secondary Objectives:
 
 To demonstrate superiority over placebo and over lurasidone alone in maintaining remission from depression in bipolar disorder. To demonstrate efficacy can be sustained with NRX-101 dosing regimens To demonstrate NRX-101 safety

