Endpoint(s)	
Primary Endpoint:
 
 The primary outcome measure will be time to relapse, defined as the need to implement a new treatment plan or a return to baseline levels on the Columbia-Suicide Severity Rating Scale (C-SSRS), or the Montgomery Asberg Depression Rating Scale (MADRS) subset on the Bipolar Inventory of Symptom Severity (BISS).
Study Design	IV Ketamine infusion followed by a double blind, placebo – controlled, parallel arm trial
Inclusion Criteria:	
A subject will be eligible for inclusion in this study only if all of the following criteria apply:
 
 Male or female, 18 to 65 years of age, inclusive, at screening. Able to read, understand, and provide written, dated informed consent prior to screening. Participants will be deemed likely to comply with study protocol and communicate with study personnel about AEs and other clinically important information. Diagnosed with Bipolar Disorder (BD) according to the criteria defined in the DSM-5. The diagnosis of BD will be made by a site psychiatrist and supported by the MINI 7.0.2. The diagnosis will be confirmed by remote, independent raters, via teleconference between the screen visit and the baseline visit. Suicidal ideation or behavior of sufficient severity to meet the requirements for a score of 4, or 5 on the C-SSRS (suicide attempt, interrupted attempt, aborted attempt, preparatory actions toward imminent suicidal behaviors, active method, intent +/- plan). A score equal to or greater than 20 on the MADRS items of the BISS. In good general health, in the opinion of the investigator, as ascertained by medical history, physical examination (PE) (including measurement of seated vital signs), clinical laboratory evaluations, and electrocardiogram (ECG). If female, a status of non-childbearing potential or use of an acceptable form of birth control per the following specific criteria: 
 Non-childbearing potential (e.g., physiologically incapable of becoming pregnant, i.e., permanently sterilized [status post hysterectomy, bilateral tubal

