7.1 Inclusion Criteria

1. Male or female, 18 to 65 years of age, inclusive, at screening.
2. Able to read, understand, and provide written, dated, informed consent prior to screening. Participants will be deemed likely to comply with study protocol and communicate with study personnel about AEs and other clinically important information.
3. Diagnosed with BD according to the criteria defined in the DSM-5. The diagnosis of BD will be made by a site psychiatrist and supported by the MINI 7.0.2. The diagnosis will be confirmed by remote, independent raters via teleconference between the screen visit and the baseline visit.
4. Suicidal ideation or behavior of sufficient severity to meet the requirements for a score of 4 or 5 on the C-SSRS.
5. A score equal to or greater than 20 on the MADRS items of the BISS.
6. In good general health, as ascertained by medical history, physical examination (PE) (including measurement of seated vital signs), clinical laboratory evaluations, and electrocardiogram (ECG).
7. If female, a status of non-childbearing potential or use of an acceptable form of birth control per the following specific criteria:
 - c. Non-childbearing potential (e.g., physiologically incapable of becoming pregnant, i.e., permanently sterilized [status post hysterectomy, bilateral tubal ligation], or is post-menopausal with her last menses at least one year prior to screening); or
 - d. Childbearing potential, and meets the following criteria:
 - iv. Childbearing potential, including women using any form of hormonal birth control, on hormone replacement therapy started prior to 12 months of amenorrhea, using an intrauterine device (IUD), having a monogamous relationship with a partner who has had a vasectomy, or is sexually abstinent.
 - v. Negative urinary pregnancy test at screening, confirmed by a negative urinary pregnancy test at randomization prior to receiving study treatment.
 - vi. Willing and able to continuously use one of the following methods of birth control during the course of the study, defined as those which result in a low failure rate (i.e., less than 1% per year) when used consistently and correctly: implants, injectable or patch hormonal contraception, oral contraceptives, IUD, double-barrier contraception, sexual abstinence. The form of birth control will be documented at screening and baseline.
8. Body mass index between 18-35 kg/m².

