Subjects who meet study criteria for relapse at any point during the study will be withdrawn from the study and offered clinically-appropriate treatment as determined by the treating study physician, which may

include inpatient hospitalization, repeated administration of ketamine, electroconvulsive therapy (ECT), or other treatments determined by professional judgment. Subjects who demonstrate therapeutic benefit from experimental drug NRX-101 (DCS+ lurasidone) at study completion may be offered prescribed DCS by their treating psychiatrist.

The Schedule of Study Activities (Table 3) summarizes the frequency and timing of efficacy, PK, and safety measurements applicable to this study. With the exception of post-dose assessments, visit-specific subject-reported outcomes assessments should be conducted or completed before any tests, procedures, or other consultations for that clinic visit to prevent influencing subject perceptions. A recommended order of study procedures will be provided to sites as a separate document.

Actual dates and times of assessments will be recorded in the source documentation and electronic Case Report Form (eCRF).

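### The MADRS criterion for relapse (20 or more, no rise needed) can count a stable or improving ketamine responder as a primary event at Day 7, and the relapse definition differs between sections

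*Combined protocol and SAP*

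**What the plan says.** All references are to the combined protocol and SAP.

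- **Entry (7.1).** "A score equal to or greater than 20 on the MADRS items of the BISS". There is no upper limit.
- **Randomisation (8.1.6; also 6.2 and 8.2.3).** At 24 hours the subject needs "a 25% or greater reduction in the on the MADRS subset of the BISS score" and a C-SSRS of 3 or less. No absolute MADRS ceiling applies.
- **Relapse (8.2.5.1.1).** Three alternatives: "a return to a score of ≥ 4 on the C-SSRS"; "a score of ≥ 20 on the MADRS subset of the BISS following a response to" ketamine at 24 hours; or the physician's decision that the treatment plan must change.
- **Consequence (8.1).** "Subjects who meet study criteria for relapse at any point during the study will be withdrawn from the study".
- **Adjudication (8.2.5.1.1).** The Relapse Adjudication Committee (RAC) checks each event against the protocol definition and may declare a relapse that the site did not. "The RAC will meet monthly".
- **Timing (Table 3).** After the 24-hour assessment the next BISS is at Day 7.

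Other sections define the endpoint differently. The Synopsis has "the need to implement a new treatment plan or a return to baseline levels on the Columbia-Suicide Severity Rating Scale (C-SSRS" and then adds the MADRS subset; 5.1 matches it. Section 11 gives the C-SSRS and MADRS criteria but no treatment-plan criterion. Section 13.5.1 has all three criteria. Sections 11 and 13.5.1 give the MADRS value as 20 without an inequality sign.

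**The concern.** The Synopsis states the primary objective as delaying relapse "following stabilization of depression and ASIB in response to initial ketamine infusion". A relapse event should then mean that something gained was lost. The C-SSRS criterion works that way: response requires 3 or less, and relapse is a return to 4 or more, so nobody is randomised already in the event state. The MADRS criterion lacks that property, because response is relative (a 25% fall) while relapse is absolute (20 or more).

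Subjects with no worsening can therefore be counted as primary events and taken off study drug. For them the endpoint records an incomplete response to open-label ketamine, not failed maintenance on the randomised drug. Separately, the same scores can give different primary events depending on the section followed.

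**Working it through.** **1. Where the two rules overlap.** Let B be the pre-ketamine score and S the 24-hour score, in whole numbers. Response requires S ≤ 0.75 × B. The MADRS relapse criterion is met at any later score of 20 or more. Both can hold when 0.75 × B ≥ 20, that is B ≥ 26.67, so from B = 27.

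| B | Highest S that is still a response |
|---|---|
| 26 | 19 |
| 27 | 20 |
| 28 | 21 |
| 30 | 22 |
| 32 | 24 |
| 36 | 27 |

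Subjects with B of 20 to 26 are unaffected. A subject scoring 30, 22, 22 is stable and meets the criterion. One scoring 30, 22, 20 is 33% below the pre-ketamine score, still improving, and also meets it.

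**2. The sections side by side.** Take 36, then 26 at 24 hours, then 24 at Day 7. Under 8.2.5.1.1 this is a relapse. Under the Synopsis and 5.1 it is not, if baseline means the subject's own score. If baseline means the entry threshold of 20, the sections agree, but this subject never left that level and so cannot return to it. The plan does not say which meaning applies. In 11 and 13.5.1 the words about returning may govern the MADRS score as well as the C-SSRS. On that reading a prior score below 20 is implied and this subject is not an event; on the other reading the subject is.

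**3. The plan's sample size (13.8.3).** Inputs are 30% relapse on NRX-101 (K/N), 70% on lurasidone (K/L), two-sided 0.05 and 90% power. The hazard ratio is ln(0.30)/ln(0.70) = 3.376. Freedman's formula gives 10.507 × (4.376/2.376)² = 35.6, so 36 events. The average relapse probability at 2:1 is 2/3 × 0.30 + 1/3 × 0.70 = 0.433, and 36/0.433 = 83.1. That reproduces 84 = 56 + 28.

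**4. Possible size.** The documents give no MADRS distribution, so every share here is assumed. With pre-ketamine means of 26 to 34 (SD 4 to 6, truncated at 20) and mean falls of 40% to 60% (SD 25 percentage points), about 4% to 36% of responders are at 20 or above at 24 hours. The table takes 10/20/30% of randomised subjects, about 11/22/34 of the 112 evaluable. The last row uses 10/20/25%, because there the share must fit within the planned 30%.

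Let g be the share of an arm still at 20 or above on Day 7 without having risen, and p the planned relapse rate. If these events come on top of p, they make up g/(g + (1 − g)p) of all events. If p already includes them, they make up g/p. Power is for K/N against K/L, 56 against 28, exponential times over 42 days, unadjusted log-rank test, by simulation. With no such subjects it is 96%. The Schoenfeld approximation gives 93%, and both exceed 90% because Freedman's formula is conservative here.

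| Assumption | Share of K/N events | Share of K/L events | Power |
|---|---|---|---|
| All persist, on top of 30%/70% | 27/45/59% | 14/26/38% | 91/83/74% |
| Half persist in each arm, on top | 15/27/37% | 7/14/20% | 94/91/87% |
| 30% persist in K/N, 70% in K/L, on top | 9/18/25% | 10/19/28% | 96% throughout |
| All persist, already within 30%/70% | 33/67/83% | 14/29/36% | about 95% |

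Section 13.8.3 does not say whether its 30% and 70% include such events.

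**The case against.** **The RAC will filter these cases.** It is told to apply the protocol definition, and nothing tells it to require a rise. It meets monthly, and nothing makes withdrawal wait for its decision.

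**Sections 11 and 13.5.1 can be read as requiring a return to 20.** That reading is fair and would exclude stable subjects. Section 8.2.5.1.1 does not carry it, so the reading adds to the ambiguity.

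**An absolute threshold equal to the entry level is a defensible exit rule for suicidal patients.** This has force as a safety argument. But the C-SSRS and treating-physician criteria already provide the exit, and neither needs to change. The question is what counts as a primary efficacy event.

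**The frequency is unknown.** This stands. The overlap is certain from the text; its prevalence is not.

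Three stronger readings are tempting and not supported:

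- *The rule inflates the false-positive rate.* The same rule applies in every blinded arm, and nothing in the documents suggests inflation.
- *The trial is underpowered because of it.* Power ranges from no loss to 74% under assumptions the documents do not settle.
- *Section 13.10.5 is one more conflicting definition.* It says that the physician judges relapse in real time, guided by baseline measures. That describes who decides and how; it does not list criteria. Sections 13.5.1 and 8.2.5.1.1 also share the same three criteria, differing mainly in how the MADRS value is worded.

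**Conclusion.** The point holds as a defect in the definition of the primary endpoint. From the text alone, any subject with a pre-ketamine MADRS subset of 27 or more can be randomised at 20 or above and, without worsening, be counted as relapsed at Day 7 and withdrawn. Also from the text alone, the sections do not agree on the definition and none is named as governing.

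How many subjects this affects is an assumption. At 10% affected and all persisting, 27% to 33% of K/N events would involve no rise, depending on whether the planned rates already include them. Misclassified primary events and ambiguity are the main harm; any loss of power is secondary and conditional. The point should be fixed before enrolment, since subjects withdrawn under the present rule cannot be put back on treatment.

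**What to change.** Use one definition in the Synopsis, 5.1, 8.2.5.1.1, 11 and 13.5.1, and apply the same one to the withdrawal rule in 8.1 and to the RAC. Relapse is any of:

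1. C-SSRS of 4 or more.
2. A physician-determined new treatment plan, excluding dose changes of study drug.
3. A MADRS subset of 20 or more in a subject who has scored below 20 at the 24-hour or any later assessment. For a subject who has not been below 20 since ketamine, the score must be 20 or more and also at least 5 points above that subject's lowest score since the 24-hour assessment.

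Checks (pre-ketamine, 24-hour, later scores):

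- Not relapses: 30-22-20, 27-20-20, 36-26-24.
- Relapses: 25-18-22, 20-15-20, 40-30-39, 36-26-10-28, 36-27-8-31.

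A responder still at 20 or above has fallen at least 7 points (27 to 20 is the smallest case), so a return to the subject's own pre-ketamine score always counts. Anchoring on the lowest score instead of the 24-hour score means a late worsening after further improvement is not missed. Keep 20 or more for everyone as a sensitivity analysis.

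**Cost.** This changes wording only, with no change to eligibility, visits or sample size. There will be somewhat fewer MADRS-triggered events, confined to subjects who have not been below 20 since ketamine. As an illustration, if relapse hazards fell by 10/20/30% in every arm, power against lurasidone would be about 95/93/91%. Power to beat both comparators would be about 90/88/84%, against 93% with no reduction. So 90% cannot be promised for the joint claim.

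The 5 points are a judgement. A course such as 40-25-30 counts as relapse although it is well short of the subject's own baseline. The 24-hour score also comes from a BISS with a 7-day recall period (8.2.6.1), so it partly reflects the days before the infusion.
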